## Day 3 - SmartPill® Cohort returns to CHOP CHPS/NGL

- All subjects maintain events diary, continue moderate fat diet
- SmartPill® cohort:
  - Takes SmartBar® study breakfast, followed by SmartPill®
  - Fasts for six hours during study

## Day 4

- Moderate fat diet
- 3-day weighed food record begins
- Food record Day 1
- Maintain adverse events diary
- SmartPill® cohort monitors for passage of capsule and returns monitoring belt upon completion of the study

#### Day 5

- Moderate fat diet
- Food record Day 2
- Stool collection begins (72-hour fecal fat), store frozen until brought to CHOP
- 72-hour stool Day 1
- Maintain adverse events diary
- SmartPill® cohort monitors for passage of capsule and returns monitoring belt upon completion of the study

#### Day 6

- Moderate fat diet
- Food record Day 3
- 72-hour stool Day 2
- Maintain adverse events diary

## Day 7

- Moderate fat diet
- 72-hour stool Day 3
- Maintain adverse events diary

#### 4.2.2 Visit 3

Visit 3 takes place over seven total days, detailed below:

#### Day 1

- Regular lunch/dinner except for no intake of dairy products
- No alcohol intake
- Normal daily activity
- Fast overnight starting at 8pm

## Day 2 – Visit to CHOP CHPS/NGL

- Insert blood-drawing intravenous catheter
- Baseline blood draw for MBT / study labs drawn (Vitamins A/E, Magnesium, essential fatty acids)
- Administer MBT study meal (breakfast)
- MBT hourly blood sample for 9 hours
- After hour 6, low-fat study lunch
- Anthropometry (height, weight, skinfolds, circumferences)
- Questionnaires: Health History and medications, Quality of life questionnaire (CF-QOL), PROMIS, GI symptom questionnaire, Adherence, Adverse Events
- Instructions will be given for collection and shipping for: stool collection (72-hour fecal fat analysis), 3-day weighed food records, and adverse events diary
- Provide arm 2 study medication
- SmartPill® cohort will fast overnight starting at 12:00am

## Day 3 - SmartPill® Cohort returns to CHOP CHPS/NGL

- All subjects maintain events diary, continue moderate fat diet
- SmartPill® cohort:
  - Takes SmartBar® study breakfast, followed by SmartPill®
  - Fasts for six hours during study

## Day 4

- Moderate fat diet
- 3-day weighed food record begins
- Food record Day 1
- Maintain adverse events diary
- SmartPill® cohort monitors for passage of capsule and returns monitoring belt upon completion of the study

#### Day 5

- Moderate fat diet
- Food record Day 2
- Stool collection begins (72-hour fecal fat), store frozen until brought to CHOP
- 72-hour stool Day 1
- Maintain adverse events diary

• SmartPill® cohort monitors for passage of capsule and returns monitoring belt upon completion of the study

## Day 6

- Moderate fat diet
- Food record Day 3
- 72-hour stool Day 2
- Maintain adverse events diary

#### Day 7

- Moderate fat diet
- 72-hour stool Day 3
- · Maintain adverse events diary

#### 4.3 Unscheduled Visits

Due to the complexity of the study, no unscheduled visits will be permitted.

#### 4.4 Concomitant Medication

All prior and concomitant medications and dietary supplements used within 14 days prior to the screening visit and through the end of the study will be recorded. The dates of administration, dosage, and reason for use will be included.

## 4.5 Subject Completion/Withdrawal

For subjects with CF and EPI who were naïve to PPI at the start of the study, at the end of participation in the study (all collections are complete for Visit 3) omeprazole will be discontinued and they will and resume their usual care without acid suppression. For subjects with CF and EPI who were receiving acid suppression with PPI or H2RA prior to the start of the study, at the end of participation in the study (all collections are complete for Visit 3), omeprazole will be discontinued and they will resume their usual care, including their acid suppression product and dose they were receiving before the study began.

Subjects may withdraw from the study at any time without prejudice to their care. They may also be discontinued from the study at the discretion of the Investigator for lack of adherence to study treatment or visit schedules, or adverse events. The Investigator or the Sponsor may also withdraw subjects who violate the study plan, or to protect the subject for reasons of safety or for administrative reasons. It will be documented whether or not each subject completes the clinical study. If the Investigator becomes aware of any serious, related adverse events after the subject completes or withdraws from the study, they will be recorded in the source documents and on the CRF.

#### 5 STUDY EVALUATIONS AND MEASUREMENTS

## 5.1 Screening and Monitoring Evaluations and Measurements

#### 5.1.1 Medical Record Review

Variables that will be abstracted from the medical record:

- Date of birth
- Sex
- Weight
- Cystic fibrosis and exocrine pancreatic insufficiency diagnoses
- Cystic fibrosis genotype
- Biochemical evidence of malabsorption including fat-soluble vitamin deficiency, essential fatty acid deficiency, and fecal elastase
- Subjective evidence of malabsorption including poor weight gain, steatorrhea, or increased stool frequency
- Past PERT use
- Past PPI or H2RA use

### **5.1.2** Laboratory Evaluations

Fecal Elastase-1: Pancreatic function will be assessed by fecal elastase-1 to determine the level of pancreatic enzyme activity in the stool. Subjects will be provided with the stool collection kit and proper instructions and supplies, and samples will be collected during the day of the visit if possible, or at home and returned. The stool sample will be stored at -  $20^{\circ}$ C, and analyzed with a monoclonal enzyme-linked immunosorbent assay (CHOP Lab). Serum retinol and  $\alpha$ -tocopherol: will be drawn at the assessment visits and assayed at Craft Laboratories.

Serum magnesium: will be drawn at the assessments visits and processed at CHOP Core Lab. There is evidence to suggest that long-term use of a PPI (>1 year) impairs magnesium absorption and may result in hypomagnesemia. This has not been noted in short-term use.

Linoleic acid (essential fatty acid panel): will be drawn at the assessment visits and assessed at ARUP Laboratories.

Any individuals from an institution outside of CHOP will receive only coded, not readily identifiable, samples for analyses and are not otherwise engaged in human subjects' research.

## 5.1.2.1 Pregnancy Testing

A urine pregnancy test will be performed for female subjects  $\geq$  9 years of age who are physically capable of becoming pregnant.

#### 5.1.3 Other Evaluations

Anthropometric Assessment: Weight, height, and BMI will be assessed at all study visits. Measures of body composition will also be conducted for relative muscle and fat at Visits 2 and 3. All anthropometric techniques will follow those described by Lohman et al. Weight (0.1kg) will be measured on a digital electronic scale (Seca, Munich, Germany) and stature (0.1cm) on a stadiometer (Holtain, Crymych, UK). Skinfold thickness will be measured (0.1mm) at the triceps, biceps, subscapular, and supra-iliac sites with a skinfold caliper (Holtain, Crymych, UK) to assess subcutaneous fat stores. Mid upper arm circumference measured with a non-stretchable fiberglass tape (0.1cm) (McCoy, Maryland Heights, MO). Upper arm muscle and fat area Z-scores will be generated.

Body Composition: Total body composition, total FFM and FM, and percent body fat (%FAT), will be assessed by the skinfolds using prediction equations adapted for children, adolescents, and adults.

Pubertal Status: Pubertal status will be determined by Tanner Stages of sexual maturity using a validated self-assessment questionnaire developed by Morris and Udry. The self-assessment questionnaire will be completed at Visit 1 by all subjects 12 to 18 years of age (assisted by a family member as needed). Female subjects will asked a series of questions to determine their menarchal status, age at first menstruation, and regularity of menstruation.

Dietary Intake: At Visit 1, a diet pattern history including the subject's clinically established PERT use will be obtained and subjects will be asked to maintain a moderate to high fat diet for the duration of the study, as well as to maintain their usual PERT use. Three-day weighed food records will be obtained at Visits 2 and 3 and calories, macro- and micro-nutrient content calculated. Subjects will be provided with scales, spoons and all supplies necessary for the collection of the dietary data and will be conducted with assistance from the CHPS staff and Bionutrition Unit. Dietary intake will be analyzed using Nutrition Data System for Research software version 2012 developed by the National Coordinating Center (NCC, University of Minnesota. Minneapolis, MN). The three-day weighed food records will coincide with the stool collection for determining the coefficient of fat absorption (see below).

Demographics and Health Questionnaire: The questionnaire will be administered via interview by the research staff, and will consist of two sections. The Health History section has general questions about the subject's health history including documentation of medical history, recent hospital admissions and illnesses, medication, history of pancreatic enzyme supplementation, and nutrient supplement use. The Health History section will be administered at all study visits. A Demographics section describes racial/ethnic status and insurance status of the research subject. In addition to subjects' contact information (name, address, phone numbers); contact information from two additional contacts will be collected to maintain contact with the subject in the event that the subject cannot be contacted at their primary residence. The demographic and contact information will be administered at Visit 1 only.

Quality of Life Questionnaires: In order to assess the health-related quality of life (QOL), validated questionnaires will be administered to all subjects at both Visits 2 and 3. The Cystic Fibrosis Questionnaire, Revised (CFQ-R, University of Miami) will be completed by the subjects. There is a questionnaire for subjects age 12-13, as well as a separate questionnaire for subjects greater than 14 years of age that is also validated in adults.

Patient Reported Outcomes (PROMIS): We will assess patient reported outcomes at both Visits 2 and 3 using the NIH-developed pediatric PROMIS short forms assessing pain, fatigue, depressive symptoms, physical function (mobility), and peer relationships. Adult subjects will use the corresponding adult forms. All subjects will use specific PROMIS short forms for GI symptoms including belly pain, diarrhea, gas and bloating, constipation, gastroesophageal reflux, and nausea and vomiting. These are valid and reliable scales broadly applicable across populations, GI symptoms, GI diseases and demographics.

Adherence: Adherence to both PERT and PPI will be assessed at study Visits 2 and 3, as well as by phone calls. This time will also be used to trouble-shoot any barriers to adherence, and also to collect information on adverse events experienced during the course of the study.

Adverse Events Diary: Subjects will be asked about all adverse events at both Visits 2 and 3, and asked to rate by intensity (mild, moderate, severe). Serious adverse events will be reported as per various policies in a timely manner to CHOP IRB, and CHPS.

## 5.2 Efficacy Evaluations

#### 5.2.1 Diagnostic Tests, Scales, Measures, etc.

Coefficient of Fat Absorption (CFA): The primary outcome, the coefficient of fat absorption (CFA%) will be determined by the 72-hour stool collections at Visits 2 and 3, and a 3-day weighed food record collection while consuming a moderate fat (about 80+ g/day) diet. These stool collections will be performed at home and returned to CHOP. Subjects will be given a home collection kit and detailed instructions. Specimens will be stored frozen until analysis of total fat content by a gravimetric method (Mayo Medical Laboratories, Rochester, MN). Total dietary intake of fat during the 3-day period will be assessed from the 3-day weighed food records which will coincide with the 72-hour stool collection, and the CFA% will be calculated. The CFA% will be compared between subjects on PPI and PERT versus PERT and placebo.

Malabsorption Blood Test (MBT): The MBT primary outcomes consist of parameters from pharmacokinetic analyses. The MBT consists of a simultaneous oral dose of pentadecanoic acid (PA), a free fatty acid, and triheptadecaenoin (THA), a triglyceride with three heptadecanoic (HA) saturated fatty acids requiring hydrolysis by pancreatic lipase before HA can be intestinally absorbed (Patent # US 7402405 B2, July 22, 2008). The MBT with the PA and THA is delivered in a breakfast test meal after a 12-hour fast and 24 hours without dairy foods. Serum concentration levels of PA and HA are assessed by gas-liquid chromatography (GC), from serum samples drawn prior to MBT and then hourly for eight hours. The MBT test meal is prepared immediately before consumption, with 5.0g of PA

and 5.5g of THA blended into a test meal composed of 64g vanilla Scandishake (Axcan Scandipharm, Birmingham, AL), 6oz Silk Light vanilla soy milk, 15mL Hershey's chocolate syrup, and 10mL microlipids (www.nestle-nutrition.com). The 8oz MBT test meal contains ~550 calories, 32 g fat, and 52% of calories from fat. The test meal was designed to be similar to a high fat dinner meal. Prior to administration of the MBT test meal, an indwelling catheter is placed for baseline (0 Hour) and subsequent blood draws at Hour 1, 2, 3, 4, 5, 6, 7, 8, and if possible, 9 post-ingestion for quantification of serum PA and HA. The MBT test meal is consumed within five minutes of the baseline blood draw. After the Hour 5 or 6 blood draw, subjects consume a 1000 kcal, low fat (12g) lunch meal, and further blood samples will follow this meal. During the protocol period, subjects are offered non-caloric and non-caffeinated beverages *ad libitum*.

Each subject will have two MBT, the first after the initial 28 day treatment course of PPI or placebo (Visit 2), and the second after completing the second 28 day treatment course of PPI or placebo (Visit 3), when subjects will be on the opposite treatment. Plasma samples will be analyzed by a GC method at Wake Forest University (Winston-Salem, NC). Utilizing the relative absorption of HA to PA, the MBT has been shown to respond to changes in fat absorption in healthy adult subjects using a lipase inhibitor and in subjects with CF and PI while on and off pancreatic enzyme therapy, and is also sensitive to enzyme dose titration.

SmartPill® – The SmartPill® (Given Imaging) is an ingestible capsule that will measure pressure, pH and temperature in the 12 subjects ≥18 years of age (Visits 2 and 3) as it travels through the gastrointestinal (GI) tract to assess GI motility and pH. The subject will be required to fast for at least 8 hours prior to the test and 6 hours after the SmartPill® is taken. The subject will be provided with a SmartBar®, which is a standardized meal replacement (similar to a granola bar) that is eaten just prior to swallowing the capsule. The specific nutritional make-up and calorie content of the bar are important for a valid test result. The capsule will travel through the GI tract and wirelessly transmit data to a recorder worn on a belt clip or lanyard. The SmartPill® capsule is 26mm x 13mm and is slightly larger than a multi-vitamin. It is naturally passed during a bowel movement, usually within a few days. The SmartPill® is FDA-approved and will be used in accordance with its approved labeling.

## 5.3 Safety Evaluation

Safety will be monitored by adverse events reporting. The frequencies of AEs by type, body system, severity and relationship to study supplement will be summarized. SAEs (if any) will be described in detail.

#### 6 STATISTICAL CONSIDERATIONS

#### **6.1** Primary Endpoint

The primary hypotheses of this study: The use of omeprazole, a proton pump inhibitor medication, in combination with PERT will significantly improve dietary fat absorption compared to placebo in subjects with CF and EPI as indicated by CFA%. Our previous experience in subjects with CF and EPI receiving PERT, CFA% was 81±14% in one study, 83±10% in another, and more recently, 89.5±7.4% in subjects with CF gating mutations and EPI. In comparison, in healthy subjects, CFA% is typically ≥93%. We will use a randomized placebo-controlled double blinded crossover trial to investigate the efficacy of omeprazole. The crossover design allows subjects to serve as their own controls to evaluate outcomes with and without omeprazole treatment.

## 6.2 Secondary Endpoints

The secondary objectives are exploratory, 1) to determine if changes in duodenal pH on and off acid suppression occur using the SmartPill®, and if such changes correlate with changes in fat absorption; 2) to characterize changes in triglyceride absorption on and off acid suppression using the MBT; 3) to explore associations among changes in nutrition status (weight, height, BMI), GI symptoms, and quality of life in subjects treated with omeprazole vs. placebo in combination with PERT.

#### 6.3 Statistical Methods

#### 6.3.1 Baseline Data

Descriptive statistics for CFA%, duodenal pH, MBT, and QOL outcomes (mean, standard deviation, median, range, 95% CI) will be calculated at baseline for the total group for continuous variables and  $\chi$ -squared or Fisher's exact tests for categorical variables. Differences between randomization groups at each time point and differences in the change over time with treatment will be assessed with unpaired t tests or Mann Whitney U rank sum tests as appropriate. For the MBT outcomes, a moment-based pharmacokinetic (PK) analysis will be performed based on non-compartmental methodology using WinNonLin version 9.1 (Pharsight, Cary, NC). Baseline ( $C_0$ ) and maximum ( $C_{max}$ ) plasma concentrations are calculated, and area under the curve from time zero to eight hours (AUC) is calculated using the linear trapezoid method. To describe HA exposure relative to that of PA, the ratio of the HA to PA  $C_{max}$  ( $C_{max}$  HA/PA) and AUC (AUC HA/PA) is calculated for each subject after molar transformation and dose-normalization of exposure metrics. Using this method, population PK modeling is conducted by simultaneously fitting structural PK models to both PA and HA concentrations.

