#### **MBT Quality Improvement Project**

The Principal Investigator (PI) ([name]) is ultimately responsible for monitoring the data integrity as well as the patient safety for this methods research development project. She will oversee all communication and scheduling prior to the MBT, participate in the consent process, and oversee all data analysis and collection.

Since the PI will be participating in this project and since other employees who report directly to the PI will be participating, we acknowledge that there is the risk of coercion. We want to make it clear that all participants were on this study prior to this amendment and are knowledgeable of the procedures and risks associated with the MBT.

Table 1: Schedule of Study Procedures Study Phase	Visit 1	Visit 2	Visit 3
July Filase	(Screening and Consent)	(Assessment 1)	(Assessment 2)
Assessment		,	,
Demographics	х		
Prior/Concomitant Medications	Х		
Randomization	Х		
Dispense Study Drug	Х	Χ	
Fecal elastase (if necessary)	X		
Urine pregnancy test	X		
Outcome Measures	-		
Coefficient of fat absorption		Χ	X
pH via SmartPill® (≥18y, n=12)		X	X
Malabsorption blood test		X	X
Serum vitamins A and E, essential fatty acids		Χ	X
Serum magnesium		Χ	X
Nutritional status			
Height, weight, BMI	X	X	X
Circumferences / skinfolds		Χ	X
Sexual maturity self-assessment (<18 y, n=12)	X		
Diet			
Diet pattern history	X		
Three-day weighed food record		X	X
Questionnaires			T
Health history	X	Χ	X
CF Quality of Life (CFQ-R)		X	X
Patient Reported Outcomes (PROMIS)		Χ	X
Demographics	X		
GI Symptom Questionnaire (PROMIS)	X	X	X
Adherence to Treatment, Enzymes		Х	X

Adverse Events	x	X
1 10 1 0 1 0 1 0 1 0 1 0 1		1

Table 2: Study Timeline

Table 2: Timeline					Yea	r 1 (	2018	3-19)									Yea	r 2 (	2019	9-20	)				
	Feb	Mar	Apr	Мау	Jun	Jul	Aug	Sept	Oct	Nov	Dec	Jan	Feb	Mar	Apr	Мау	Jun	Jul	Aug	Sept	Oct	Nov	Dec	Jan	Total
Start-up	Х	Х	Х	Χ	Χ																				
Visit 1: Consent				1	1	1	1	2	2	2	2	2	2	2	2	2	2								24
Visit 2: Assessment 1					1	1	1	1	2	2	2	2	2	2	2	2	2	2							24
Visit 3: Assessment 2							1	1	1	1	2	2	2	2	2	2	2	2	2	2					24
Visit Total				1	2	2	3	4	5	5	6	6	6	6	6	6	6	4	2	2					72
Sample and Data Analysis									X	Χ	Χ	Χ	Х	Χ	Χ	Χ	Χ	Χ	Χ	Х	Χ	Χ	Χ	Χ	
Closeout																							Χ	Х	

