## 6.3.2 Efficacy Analysis

Descriptive statistics for CFA%, duodenal pH, MBT and QOL outcomes (mean, standard deviation, median, range, 95% CI) will also be calculated for the total group comparing on and off omeprazole treatment using pair t-tests or Wilcoxon sign rank tests as appropriate. Changes within randomization groups over time will also be explored using paired t tests Differences between randomization groups (12 randomized initially to placebo vs. 12 to omeprazole treatment) on visit 1 will also be tested using unpaired t tests or Mann Whitney U rank sum test as appropriate. Significance of the differences on and off treatment assessed with paired t tests or Wilcoxon sign rank tests as appropriate. PK parameters can then be compared for the total group comparing on and off omeprazole treatment using pair t-tests or Wilcoxon sign rank tests as appropriate, and between randomization groups at each time point using an unpaired t-test or Mann Whitney U rank sum test as appropriate. Alternately, population PK analyses for repeated-measures endpoints can be conducted via nonlinear mixed-effects modeling with a qualified installation of the nonlinear mixed-effects modeling (NONMEM) software, Version VII, Level 2.0 (ICON Development Solutions, Hanover, MD). HA and PA concentrations will be transformed to molar quantities and the ratios for HA to PA Cmax and AUC and the associated 95% confidence interval will be calculated. A mixed-effects modeling approach will be employed to examine the correlation of subject characteristics (age, BMI, sex, disease status, etc) to CFA%, duodenal pH, QOL parameters and to PA and HA exposure metrics derived from the non-compartmental analysis to assess change over time in MBT response to PERT administration in subjects with CP. Metrics to be tested will be CFA%, duodenal pH, QOL parameters, PA and HA Cmax, AUC, HA/PA Cmax and AUC ratio and the %HA response comparing subjects when on or off omeprazole treatment and also comparing randomization groups at each time point. A value of p<0.05 will be considered statistically significant.

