There is limited evidence from randomized placebo-controlled trials that agents such as omeprazole that reduce gastric acidity, when used as adjunctive therapy with PERT are associated with improvement in fat absorption. Heijerman and colleagues, in a randomized controlled trial with a crossover design, found a reduction of 4.8% in fecal fat excretion in 11 subjects receiving 14-days of omeprazole compared to when they received 14-days of placebo (18.1 % vs. 22.9%, respectively). In another study using a similar crossover design, the same authors found a reduction in fecal fat excretion of 8.9%, from 19.6% after 14-day placebo treatment to 10.7% after 14-day omeprazole treatment in 9 subjects on high dose pancreatic enzyme therapy. Proesmans et al, using a randomized crossover design in a study of 15 children with CF and confirmed steatorrhea, found a reduction 7.5 g of fecal fat (from 13.0 to 5.5 g) and an increase in CFA of 7% (from 87 to 94%) after one month of omeprazole use. In other clinical trials of H2 acid blockers as adjunctive therapy to PERT, CFA% improved from 77.1 to 83.6% in a study of 10 children with CF receiving PERT only, compared to PERT plus cimetidine over 14-day periods, and from 74.4% to 87.3% in 10 CF children receiving PERT only and PERT plus famotidine over 6-month periods. In our proposed randomized controlled trial with a crossover design, 22 subjects (11 randomized to 28-day treatment and 11 to placebo at Visit 1, then crossing over to the alternate treatment for 28-days) will have 80% power to detect an increase of 3% with omeprazole treatment compared to no change (0%) when on placebo with a common SD of 5% using a paired t-test with  $\alpha$  =0.05.

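### Section 6.3.1 plans baseline statistics for outcomes first measured after 28 days of treatment, and the plan does not define or designate the between-sequence contrast that would protect CFA% from a period effect

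*Combined protocol and SAP*

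**What the plan says.** Section 6.3.1 (Baseline Data) opens: "Descriptive statistics for CFA%, duodenal pH, MBT, and QOL outcomes (mean, standard deviation, median, range, 95% CI) will be calculated at baseline". This summary pools the two sequences. The next sentence compares the randomization groups at each time point and adds that "differences in the change over time with treatment will be assessed with unpaired t tests" or a rank-sum test. The synopsis repeats that second sentence.

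Section 6.3.2 (Efficacy Analysis) lists several comparisons:
- The on/off comparison: statistics "will also be calculated for the total group comparing on and off omeprazole treatment using pair t-tests or Wilcoxon sign rank tests".
- Within sequence: "Changes within randomization groups over time will also be explored using paired t tests".
- Between sequences: "Differences between randomization groups (12 randomized initially to placebo vs. 12 to omeprazole treatment) on visit 1 will also be tested". This sentence names no outcome.
- A closing list of metrics, including CFA%, to be tested by "comparing subjects when on or off omeprazole treatment and also comparing randomization groups at each time point", with p<0.05 as the threshold.

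Section 6.4 bases the sample size on a paired t-test in 22 subjects: a 3-point gain in CFA%, a common SD of 5 and 80% power.

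**The concern.** An analysis at baseline needs a measurement before treatment. If the outcomes have none, the 6.3.1 summary cannot be produced. If Visit 2 values were substituted, the total-group baseline would describe subjects of whom half are on omeprazole.

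A two-period crossover must also separate the drug effect from any general shift between Visit 2 and Visit 3. A within-sequence change cannot do so. A pooled on/off comparison does so only on average, when the two sequences finish equal in size, and the shift still adds noise. At stake are how the exploratory p-values are read and, for the primary endpoint, power and a possible small bias.

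**Working it through.** **1. When each outcome is measured**

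| Outcome | Source | First measured |
|---|---|---|
| CFA% | Table 1; 5.2.1 | Visit 2 |
| Duodenal pH (subjects 18 and over) | Table 1; 5.2.1 | Visit 2 |
| MBT | Table 1; 5.2.1 | Visit 2 |
| QOL (CFQ-R) | Table 1; 5.1.3 | Visit 2 |

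Sections 3.1.2 and 4.2 place Visit 2 after 28 days of assigned treatment. So 0 of the 4 outcomes has a pre-treatment value. The C0 value that 6.3.1 calls baseline is the pre-meal sample on each MBT day, not a pre-treatment value.

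**2. The Visit 1 group test.** It cannot be run for these outcomes. It may be a slip for the first assessment, since Table 2 labels "Visit 2: Assessment 1". It may instead use Visit 1 as the time of randomization, as 6.4 does: "11 randomized to 28-day treatment and 11 to placebo at Visit 1". If Visit 2 is meant, the comparison is already covered by the tests at each time point.

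**3. The plan's own sample size.** Taking 5 as the SD of the paired differences, the normal formula gives n = (5 × (1.960 + 0.842) / 3)² = 21.8, so 22, with 80.4% power. The exact two-sided t-test at n = 22 gives 76.5%, which is the reference below.

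**4. Model.** Let τ be the drug effect and π the shift from Visit 2 to Visit 3. The documents give no π, so 0, 1, 2 and 3 CFA points are assumed.
- Visit 3 minus Visit 2: placebo-first τ + π; omeprazole-first −τ + π.
- On minus off: placebo-first τ + π; omeprazole-first τ − π.

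**5. Within-sequence paired test.** With n = 11, τ = 0 and 10 df, the noncentrality is π / (5/√11).

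**6. Pooled on/off paired test.** The mean is τ + π(n₁ − n₂)/(n₁ + n₂), with n₁ placebo-first and n₂ omeprazole-first. At 11/11 the bias is 0. At 12/10 it is +2/22 = +0.09π, and at 10/12 it is −0.09π. The period effect also widens the spread: at 11/11 the expected variance of the differences is 25 + π² × 22/21, so at π = 3 the SD is about √34.4 = 5.9.

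**7. Between-sequence unpaired test of Visit 3 minus Visit 2.** The difference in means is (τ + π) − (−τ + π) = 2τ, so π cancels. The noncentrality at τ = 3 is 6 / (5 × √(2/11)) = 2.81. The pooled test with π = 0 has the same value, 3 / (5/√22) = 2.81. The degrees of freedom are 20 against 21.

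Results at SD 5 (pooled figures for π > 0 and at unequal sequences by simulation, the rest exact):

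| Test | π=0 | π=1 | π=2 | π=3 |
|---|---|---|---|---|
| Within-sequence, τ=0, % significant | 5 | 9 | 22 | 44 |
| Pooled 11/11, type I error, % | 5.0 | 4.6 | 3.5 | 2.3 |
| Pooled 11/11, power at τ=3, % | 77 | 75 | 71 | 65 |
| Pooled 12/10, power, % | 76 | 78 | 77 | 73 |
| Pooled 10/12, power, % | 77 | 73 | 66 | 56 |
| Between-sequence, power, % | 76 | 76 | 76 | 76 |

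Between-sequence power is 76.3% at 11/11 and 76.0% with a 12 to 10 split, with 5% type I error at every π.

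**8. Why change must be defined.** If change in 6.3.1 were read as on minus off, the group difference would be (τ + π) − (τ − π) = 2π. The same test would then measure the period effect. At 11/11, SD 5 and no drug effect, it would be significant in about 15%, 43% and 76% of trials at π = 1, 2 and 3.

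**9. Sensitivity.** Section 6.4 does not say whether 5 is the SD per period or of the differences. If it is per period with no correlation, the SD of differences is 5 × √2 = 7.07. For π = 0, 1, 2 and 3, the within-sequence rates become 5%, 7%, 14% and 25%, and pooled power at 11/11 is 48%, 47%, 45% and 41%. Between-sequence power is 47%.

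**The case against.** A reader might infer that the plan has no period-adjusted contrast. The documents do not support that: 6.3.1 and the synopsis both plan an unpaired comparison of change between the randomization groups, which removes the period effect if change is Visit 3 minus Visit 2. What stands is narrower. In the body of the plan the comparison sits under Baseline Data, change is undefined, and nothing designates it as the omeprazole contrast. The mixed model in 6.3.2 names subject characteristics but no period or sequence term.

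A reader might also infer that the primary test risks false positives. It does not in these settings. At 11/11 it is unbiased and its type I error falls below 5%. With a 12 to 10 split and π = 3, the error is still only about 2.7%.

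The baseline wording looks like a drafting slip. The parallel synopsis sentence omits the word, and the slip does not touch the primary test. The Visit 1 test may not be meant for these outcomes at all. The within-sequence tests are called exploratory, are not the sample-size test, and are not said to estimate the drug effect. All of this is fair and limits the consequence, but the text still needs correcting.

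Finally, a shift of 3 points equals the whole target effect, while diet and PERT are held constant and each period follows a 14-day lead-in or washout. At π = 1 the pooled test loses only about 1 to 2 points of power at 11/11, and an unequal split biases it by only 0.09 points. That stands, and it keeps the point moderate. The remedy is nevertheless almost free.

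**Conclusion.** The concern holds in a limited form. The schedule alone settles that the 6.3.1 baseline statistics cannot be produced for CFA%, duodenal pH, MBT or CFQ-R, and that the Visit 1 group test cannot be run for them if it is meant to cover them. Both are low-impact wording faults. It follows from the design that the within-sequence tests mix drug and period.

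For the primary endpoint, the weakness is reliance on a pooled test without a period term while a suitable contrast is left undefined and undesignated. With balanced completers the cost is power only: about 1, 5 and 12 percentage points at shifts of 1, 2 and 3. A 12 to 10 split of the 22 expected completers, which nothing in the plan rules out, adds a bias of about 0.09 times the shift, or 0.27 points at a shift of 3. The direction depends on which sequence loses more subjects.

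These sizes rest on assumed period shifts, on 5 being the SD of the differences, on two-sided testing at 0.05, and on no carryover after the 14-day washout.

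**What to change.** (a) In 6.3.1, limit baseline statistics to variables collected at Visit 1, such as demographics, health history, height, weight, BMI, diet pattern and the GI symptom questionnaire. Remove CFA%, duodenal pH, MBT and QOL from that sentence.

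(b) In 6.3.2, for these outcomes, change the Visit 1 group comparison to Visit 2 (first period) and label it descriptive, or restrict it to Visit 1 variables.

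(c) Report within-sequence Visit 3 minus Visit 2 changes as means with 95% confidence intervals, without tests of drug effect.

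(d) Move the between-sequence comparison of change into 6.3.2 and define change as Visit 3 minus Visit 2. State that half the difference in mean change, placebo-first minus omeprazole-first, estimates the omeprazole effect. Prespecify this as the primary CFA% test, with the pooled paired test as supportive, so that it is clear which of the two governs. State the no-carryover assumption.

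The cost is wording and one degree of freedom (20 against 21 at 22 completers). With no period effect, power is 76.3% against 76.5%, a loss of about 0.2 percentage points. No visits, samples or subjects are added.
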